# 9.2. Sample Size Determination

The sample size for this study is determined empirically based on feasibility and regulatory recommendation. Sufficient numbers of patients will be enrolled and dosed to obtain approximately 38 PK evaluable subjects (approximately 16 subjects in normal group, 8 patients each in mild and moderate groups, and 6 in severe group).

Subjects may be replaced if not PK evaluable.

## 9.3. Analysis of Pharmacokinetics and Pharmacodynamics

# 9.3.1. Analysis of Pharmacokinetics

PK analysis could be performed and PK results could be reported after all patients complete PK collection. See Section 3.1.

# 9.3.2. Derivation of Pharmacokinetic Parameters Prior to Analysis

Pharmacokinetic parameters will be derived from the lorlatinib and metabolite(s) concentration-time profile as described in Table 8.

Parameter	Definition	Method of Determination
AUC last	Area under the plasma concentration-time profile from time zero to the time of the last quantifiable concentration (C last )	linear-log trapezoidal method
AUC 24	Area under the plasma concentration-time profile during one dosing interval (24 hours)	linear-log trapezoidal method
C max	Maximum plasma concentration	Observed directly from data
C min	Minimum plasma concentration	Observed directly from data
T max	Time for C max	Observed directly from data as time of first occurrence
Tlast	Time or C last	Observed directly from the data as time of the last quantifiable concentration
CL/F	Apparent clearance	Dose/AUC 24 at steady-state
MRAUClast	Metabolite ratio for AUC last	(AUClast/MW)metabolite/(AUClast/MW)lorlatinib
MRAUC 24	Metabolite ratio for AUC 24	(AUC24/MW)metabolite/(AUC24/MW)lorlatinib
MRC max	Metabolite ratio for C max	(Cmax/MW)metabolite/(Cmax/MW)lorlatinib

 Table 8.
 Pharmacokinetic Parameter Derivation

MW= molecular weight; F= oral bioavailiability

Actual PK sampling times will be used in the derivation of PK parameters. In the case that actual PK sampling times are not available, nominal PK sampling times will be used in the derivation of PK parameters.

# 9.3.3. Statistical Methods

One-way analysis of variance (ANOVA) will be used to compare the natural log transformed AUClast, AUC24 and Cmax at steady state for each of the hepatic impairment groups (Test) to the corresponding normal hepatic function group with the same dosing schedule (Reference). Estimates of the mean differences (Test-Reference) and corresponding 90% confidence intervals for all comparisons will be obtained from the model. The mean differences and 90% confidence intervals for the differences will be exponentiated to provide estimates of the ratio of geometric means (Test/Reference) and 90% confidence intervals for the ratios.

The PK parameters (defined in Table 8) Cmax, Cmin, AUClast, AUC24, Tmax, CL/F, MRAUClast, MRAUC24, MRCmax, for lorlatinib and its metabolite(s), as appropriate, will be summarized descriptively by analyte, hepatic function group and cycle. For lorlatinib AUClast, AUC24 and Cmax, individual patient parameters will be plotted by hepatic function group and cycle. For AUClast, AUC24 and Cmax box-whisker plots of the parameters will be plotted by analyte and hepatic impairment group.

Individual concentrations in plasma will be listed and summarized descriptively by analyte, hepatic function group, cycle and nominal PK sampling time. Individual patient concentration-time data will be plotted by hepatic function group and cycle. Median profiles of the concentration-time data will be presented by hepatic function group and dose level with all hepatic function groups plotted together with separate plots for each analyte and each cycle.

For summary statistics and summary plots by sampling time, the nominal PK sampling time will be used; for individual subject plots by time, actual PK sampling time will be used.

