- 18. Serious and non-serious adverse event monitoring: AEs should be documented and recorded at each visit using the National Cancer Institute Common Terminology Criteria for Adverse Events (NCI CTCAE) version 4.03. The time period for actively eliciting and collecting AEs and SAEs ("active collection period") for each patient begins from the time the patient provides informed consent through and including a minimum of 28 calendar days after the last lorlatinib administration. If the patient begins a new anticancer therapy, the period for recording non-serious AEs on the CRF ends at the time the new treatment is started. However, any SAEs occurring during the active collection period must still be reported to Pfizer Safety and recorded on the CRF, irrespective of any intervening treatment.
- 19. Concomitant Treatments: All concomitant medications and NonDrug Supportive Interventions should be recorded on the CRF from 28 days prior to start of the study treatment and up to 28 days after the last dose of study treatment.
- 20. Suicidal Ideation and Behavior: An assessment of suicidal ideation and behavior via the Columbia Suicide Severity Rating Scale (C- SSRS) will be administered to patients prior to the first day of investigational drugs dosing (ie, Cycle 1 Day1) and then prior to dosing on Day 1 of Cycle 2 through Cycle 6. After Cycle 6 Day 1, this test will be administered prior to dosing on Day 1 of every other cycle (ie, Cycle 8 Day 1, Cycle 10 Day 1, etc.) and at EOT.
- 21. **Pharmacokinetics** plasma samples for characterization of pharmacokinetics (PK) of lorlatinib and its metabolite(s) will be collected at times 0 (predose), 0.5, 1, 2, 4, 6, 10, and 24 hours post lorlatinib dose on Cycle 1 Day 1 and Cycle 2 Day 1. Predose PK samples will also be collected prior to the lorlatinib dose on Days 8 and 15 of Cycle 1.
- 24. End of Treatment/Withdrawal: Obtain these assessments if not completed during the previous 3 weeks on study (last 6 weeks for tumor assessments). If the subject withdraws from lorlatinib treatment during a cycle visit, then this will be considered the subject's End of Treatment visit.

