## 5.4. Administration

All trial treatments will be administered on an outpatient basis.

A cycle is defined as 21 days, irrespective of any dose delays/dosing interruptions or missed doses which may affect nominal days of each cycle.

Lorlatinib will be administered orally QD at approximately the same time of the day on a continuous daily dosing schedule, ie, without a break in dosing in the absence of drug-related toxicity. Patients must swallow the study medication whole and must not manipulate or chew the medication prior to swallowing. A dosing card will be provided to the patients to provide guidance for the correct use of lorlatinib. Patients must be instructed that should they miss a dose or vomit any time after taking a dose, they must not "make it up" with an extra dose. Instead, resume the subsequent doses as originally prescribed. Any missed dose may be taken up to 6 hours prior to the next scheduled lorlatinib dose, otherwise it should be skipped and dosing resumed with subsequent doses as prescribed. The patient must be instructed to record all doses (including missed or vomited) in a dosing diary supplied by the site. If doses are missed or vomited, this must be indicated in the source documents and Case Record Forms (CRFs).

On PK sampling days, the lorlatinib dose should be taken in the clinic under the supervision of the study site personnel. The lorlatinib dose should be administered after the 0 hour (predose) PK sample has been collected (within 15 minutes prior to lorlatinib dosing). On ECG assessment days, the lorlatinib dose should also be taken in the clinic under the supervision of the study site personnel so that timing of assessments is appropriately synchronized.

Since no clinically meaningful effect of food on the PK of lorlatinib has been observed, lorlatinib can be administered with or without food.

Lorlatinib treatment may continue until confirmation of disease progression, patient refusal, or unacceptable toxicity despite of dose reduction or interruption, whichever occurs first.

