3.4.2.2. PK Parameter Analysis Set

The PK parameter analysis set is defined as all enrolled patients treated who have sufficient information to estimate at least 1 of the PK parameters of interest.

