3.4.2.3. PK evaluable Analysis set

The PK evaluable analysis set is defined as all patients in the PK parameter analysis population who have (1) completed Cycle 2 Day 1 PK collection; (2) received lorlatinib dose on Cycle 2 day 1; (3) received at least 80% of total dose within 14 days prior to Cycle 2 Day 1; (4) no dose reduction in the first cycle.

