One-way analysis of variance (ANOVA) will be used to compare the natural log transformed AUC_{24} , AUC_{last} and C_{max} of lorlatinib at steady state for each of the hepatic impairment groups (Test) to the corresponding normal hepatic function group with the same dosing schedule (Reference). Group B (Test) will be compared to Group A1 (Reference) and Group C (Test) will be compared with Group A2 (Reference). If a decision has been made to use the same dose for severe and moderate patients, the half of the control Group A2 will be matching Group C and half will be matching Group D (test), and the corresponding pairwise comparisons will be made. Additionally, Group D will be compared to Group A1 (Reference), and Group C will be compared with A1. Estimates of the mean differences (Test-Reference) and corresponding 90% confidence intervals will be obtained from the

model. The mean differences and 90% confidence intervals for the differences will be exponentiated to provide estimates of the ratio of geometric means (Test/Reference) and 90% confidence intervals for the ratios.

Residuals from the models will be examined for normality and the presence of outliers via visual inspection of plots of residuals vs predicted values and normal probability plots of residuals but these will not be included in the clinical study report. If there are major deviations from normality or outliers then the effect of these on the conclusions will be investigated through alternative transformations and/or analyses excluding outliers. Justification for any alternative to the planned analysis will be given in the report of the study.

The following PK parameters will be summarized descriptively by analyte, hepatic function group and at C1D1 and C2D1 for lorlatinib and its metabolites.

| Parameter | Summary statistics |
|--|--|
| AUC _{24,} AUC _{last} , C _{max} , C _{min} , CL/F, MRAUC _{24,} MRAUC _{last} , MRC _{max} | N, arithmetic mean, median, cv%, standard deviation, minimum, maximum, geometric mean. |
| T _{max} | N, median, minimum, maximum. |

Box and whisker plots for individual subject parameters (lorlatinib AUC $_{24}$, AUC_{last} and C_{max}) will be presented against hepatic function group by analyte and overlaid with geometric means.

PK parameter analysis set will be used for performing the analysis.

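### Steady-state AUClast in the ANOVA repeats AUC24 when the 24-hour sample is quantifiable and is a 0-10 hour area when it is not, so the secondary AUClast ratio can be biased if that loss is unbalanced

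*Protocol*

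**What the plan says.** Protocol 9.3.3 and SAP 5.1.1.1 put three lorlatinib parameters into the one-way ANOVA: "natural log transformed AUC last , AUC 24 and C max at steady state". Each comparison is reported as a ratio of geometric means with a 90% confidence interval. AUC24 and Cmax at steady state are the primary endpoints; steady-state AUClast is secondary (Protocol 2, SAP 3.1 and 3.2).

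Protocol Table 8 defines AUClast as the area from "time zero to the time of the last quantifiable concentration", and AUC24 as the area under the "profile during one dosing interval". For the first day of each of the first two cycles, footnote 21 of the Schedule of Activities says that samples "will be collected at times 0 (predose), 0.5, 1, 2, 4, 6, 10, and 24 hours post lorlatinib dose". Actual sampling times are used to derive the parameters, and Protocol 7.2.1 does not count a deviation of up to 10% of nominal time as a protocol deviation.

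On the population, SAP 5.1.1.1 ends: "PK parameter analysis set will be used for performing the analysis". SAP 3.4.2.2 admits to that set any treated patient with "sufficient information to estimate at least 1 of the PK parameters of interest". The narrower PK evaluable set in SAP 3.4.2.3 does ask for a full profile (its first condition is "1) completed Cycle 2 Day 1 PK collection"), but it is not the set named for this analysis.

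**The concern.** AUClast has no fixed upper limit; it stops wherever the patient's last quantifiable sample falls. After 10 hours the next planned sample is at 24 hours. A patient whose 24-hour sample is missing or below quantification therefore has an AUClast covering 10 hours, while the others cover about 24. The ANOVA would treat the two as the same quantity, and no rule requires a common end time.

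The 24-hour draw requires a return the next day. Protocol 5.4 states: "All trial treatments will be administered on an outpatient basis". The visit columns of the Schedule of Activities contain no Day 2, so some loss of that sample is plausible, although the documents do not quantify it.

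At stake is a secondary result printed beside the primary one. With complete sampling it tells the reader almost nothing that AUC24 does not. With incomplete sampling it may differ from the AUC24 ratio for reasons of attendance rather than liver function.

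**Working it through.** **1. Checks on the plan's own figures.** Group sizes: 4 × 8 + 6 = 38, the stated PK-evaluable total. Protocol Table 3, multiple doses at 100 mg QD: CL/F = dose/AUC gives 100000/5121 = 19.53 L/hr (stated 19.52) and 100000/5650 = 17.70 (stated 17.70). The AUC inputs are consistent.

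**2. When the 24-hour sample exists.** At 24.0 hours AUClast = AUC24. A 10% tolerance allows 21.6 to 26.4 hours. One-compartment steady-state profiles with half-lives of 8 to 27.2 hours then give AUClast/AUC24 between 0.92 and 1.07. That spread reflects clock time, not hepatic function.

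**3. When it does not: f = AUC0-10/AUC24.** The documents give no value, so f was modelled with the linear-log trapezoid on the protocol's sampling grid. The absorption rate (2 per hour) and the steady-state half-lives are assumptions; Table 3 lists no multiple-dose half-life.

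- One-compartment, half-life 27.2 down to 8 hours: f = 0.48 to 0.65.
- Bi-exponential, matched to the stated AUC and Cmax (5121 and 550.2, or 5650 and 576.5), with assumed terminal half-lives of 12 to 24 hours and initial half-lives of 1 to 4 hours: f = 0.57 to 0.71.

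The one-compartment profiles fit the stated peak poorly. Stated Cmax/AUC is 550.2/5121 = 0.107 and 576.5/5650 = 0.102. The model gives 350/5105 = 0.069 at a half-life of 12.5 hours and 272/5115 = 0.053 at 27.2 hours. Protocol 1.2.1.2.1.1 also describes a bi-exponential decline. I therefore take f = 0.5 to 0.7 as the working range.

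**4. Effect on the ratio.** With mT of nT Test profiles and mR of nR Reference profiles truncated, and the same f in both groups, the geometric mean ratio is multiplied by f^(mT/nT − mR/nR). For n = 8 per group:

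| Truncated profiles | f = 0.5 | f = 0.7 |
|---|---|---|
| 1 in Test only | 0.5^(1/8) = 0.92 | 0.7^(1/8) = 0.96 |
| 2 in Test only | 0.5^(2/8) = 0.84 | 0.7^(2/8) = 0.91 |
| 1 in Reference only | 1.09 | 1.05 |
| 2 in Reference only | 1.19 | 1.09 |
| Equal numbers in both | 1.00 | 1.00 |

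Smaller groups are more sensitive. One truncated profile in 6 (the planned Group D size) gives 0.89 to 0.94. If half of Group A2 serves as a reference of 4, one truncated profile there gives 1.09 to 1.19.

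**5. Precision.** Two groups of 8 were simulated with f = 0.60 and CV 39% (Table 3, Phase 2 multiple doses):

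| Truncated (Test, Reference) | Ratio | Coverage of 90% CI | Median CI half-width factor |
|---|---|---|---|
| 0, 0 | 1.00 | 0.90 | 1.38 |
| 1, 0 | 0.94 | 0.90 | 1.41 |
| 2, 0 | 0.88 | 0.865 | 1.43 |
| 1, 1 | 1.00 | 0.93 | 1.43 |
| 2, 2 | 1.00 | 0.945 | 1.47 |

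Balanced loss leaves the ratio alone and widens the interval.

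**6. Do other rules stop it?** SAP 4.3.2 sets parameters that cannot be derived to missing, but a 10-hour AUClast can be derived and meets its own definition. The same section removes estimates known to be biased, with vomiting as the example. SAP 5.4.2.2 permits, but does not require, exclusion of patients with events affecting their profile. Neither names a truncated AUClast. Replacing a non-evaluable patient does not take that patient out of the PK parameter set.

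**The case against.** The strongest reply is that the plan already aims at complete profiles. Protocol 3.1 and SAP 2.2 size the final analysis on patients who complete Cycle 2 Day 1 sampling, and provide for replacing the rest. On that view the root problem is the set named in SAP 5.1.1.1, and using the PK evaluable set would largely cure it. That stands, and it is one of the acceptable fixes. It does not remove the point, because the SAP as written names the wider set.

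Replacement also dilutes the effect: a truncated patient would be one in 9 rather than one in 8, giving 0.5^(1/9) = 0.93 to 0.7^(1/9) = 0.96. The discretionary exclusions might also catch the case, but a stated rule is better than case-by-case judgement in an open-label study.

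A reader might infer three stronger things that the documents do not support:

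- **That the AUClast ratio will be biased, and downward, because impaired patients miss the return visit more often.** No missing-sample rate is given for any group, all groups are patients with advanced cancer, and the shift depends on the difference in loss. It can go either way or be nil.
- **That the plan forgot the 24-hour draw.** Footnotes 14 and 21 and the sampling schema schedule it explicitly under Cycle 2 Day 1, and Protocol 7.2.1 allows a sample that cannot be taken to be re-scheduled.
- **That the primary conclusion is at risk.** The AUC24 and Cmax comparisons do not use AUClast, and SAP 4.1 plans no formal hypothesis test.

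**Conclusion.** The point holds as a minor, conditional defect in a secondary analysis. At steady state the AUClast comparison is nearly redundant when sampling is complete and mixes 10-hour with roughly 24-hour areas when it is not; the named analysis set lets the second case in.

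Its size rests on the assumed f of 0.5 to 0.7 and on assumed counts of lost samples. Two truncated profiles out of 8, all in Test, would lower the ratio by 9% to 16%; equal loss would cost only precision. The range for f comes from 100 mg QD data in patients not selected for hepatic impairment. Slower elimination would lower f, and if f differed between groups, equal loss would not cancel exactly. A 24-hour value below quantification would have the same effect as a missing one. Modelled 24-hour concentrations at 100 mg QD are about 50 to 160 ng/mL, but the quantification limit is not given, so that route cannot be assessed.

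**What to change.** In Protocol 9.3.3 and SAP 5.1.1.1, do one of the following before database release:

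- drop steady-state AUClast from the ANOVA, leaving AUC24 and Cmax; or
- keep it, restricted to profiles whose last quantifiable concentration is the nominal 24-hour sample.

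Running the AUClast comparison on the PK evaluable set would largely achieve the same, though it would not by itself cover a 24-hour value below quantification. Keep AUClast in the listings either way. MRAUClast is not in the ANOVA; its descriptive summary could carry the same restriction, if wanted.

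The cost is about one line in each document. Protocol 9 lets the SAP modify the planned analyses and asks for an amendment only for major changes to the primary endpoints, so the SAP can carry the change first. The downside is that a truncated profile no longer contributes to the AUClast comparison. It would be sensible to state in the same edit how AUC24 is derived, or set to missing, when the 24-hour sample is absent, because neither document says so explicitly.

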## 9.4. Safety Analysis

The safety analysis population will be the primary population for evaluating patient characteristics, treatment administration, and safety.

Safety data will be reviewed on an ongoing basis during the study. Safety data will be presented in tabular and/or graphical format and summarized descriptively, where appropriate.

# **Adverse Events**

Adverse Events (AEs) will be coded by system organ class (SOC) and preferred term according to Medical Dictionary for Regulatory Activities (MedDRA) terminology. AE severity will be graded according to NCI Common Terminology Criteria for Adverse Events (CTCAE) version 4.0.3.

A listing of all AEs including detailed information collected for each AE (description of event, onset date/time, duration, seriousness, severity, relationship to study drug, action taken, clinical outcome) will be presented.

The number and percentage of patients who experienced any: AE, serious AE (SAE), treatment related AE, and treatment related SAE will be summarized. Emphasis in the analyses will be placed on AEs classified as treatment emergent. The analyses will summarize AEs both on the entire study period and by cycle (Cycle 1 and Cycles beyond 1).

Additional summaries of adverse events (AE) and of other safety data will be presented in tabular and/or graphical format and summarized descriptively, as appropriate.

#### Laboratory Test Abnormalities

The number and percentage of patients who experienced laboratory test abnormalities will be summarized according to worst toxicity grade observed for each laboratory assay. The analyses will summarize laboratory tests both on the entire study period and by cycle (Cycle 1 and Cycles beyond 1). Shift tables will be provided to examine the distribution of laboratory toxicities.

For laboratory tests without CTCAE grade definitions, results will be categorized as normal, abnormal, or not done.

#### 9.4.1. Electrocardiogram

The analysis of ECG results will be based on patients in the safety analysis set with baseline and on-treatment ECG data.

ECG measurements (an average of the triplicate measurements) will be used for the statistical analysis and all data presentations. Any data obtained from ECGs repeated for safety reasons after the nominal time-points will not be averaged along with the preceding triplicates. Interval measurements from repeated ECGs will be included in the outlier analysis (categorical analysis) as individual values obtained at unscheduled time points.

QT intervals will be corrected for heart rate (HR) (QTc) using standard correction factors (ie, Fridericia's (default correction), Bazett's, and possibly a study-specific factor, as appropriate). Data will be summarized and listed for QT intervals, HR, RR intervals, PR intervals, QRS intervals, and QTcF (and other correction factors, eg, QTcB as appropriate) by hepatic function and dose. Individual QT (all evaluated corrections) intervals will be listed by study hepatic function, time and dose. The most appropriate correction factor will be selected and used for the following analyses of central tendency and outliers and used for the study conclusions. Descriptive statistics (n, mean, median, standard deviation, minimum, and maximum) will be used to summarize the absolute corrected QT interval and changes from baseline in corrected QT after treatment by hepatic function, dose and time point. For each patient and by treatment, the maximum change from baseline will be calculated as well as the maximum post-baseline interval across time-points. Categorical analysis will be conducted for the maximum change from baseline in corrected QT and the maximum post-baseline QT interval.

Shift tables will be provided for baseline vs worst on treatment corrected QT (one or more correction methods will be used) using maximum CTCAE Grade. Shift tables will also be provided for ECG abnormality at baseline vs. on treatment (yes, no, not done: (n, %)). Patients experiencing clinically relevant morphological ECG changes will be summarized (including frequency and percentage).

The effect of drug concentrations on corrected QT change from baseline may be explored graphically. Additional concentration-corrected QT analyses may be performed. Data may be pooled with other study results and/or explored further with PK/PD models. The results of such analyses will not be included in the study report.

Predose ECG on Cycle 1 Day 1 will be used as baseline for all related analysis. If the predose ECG on Cycle 1 Day 1 is not available, the ECG collected closest to Cycle 1 Day 1 (prior to the first lorlatinib dose) will be sued as baseline.

